### Aim 2 (Secondary Outcomes)

- (a) ROSE, as compared to control, will result in greater positive affect and well-being at 6-weeks, 3, 6- and 12-months follow up;
- (b) ROSE, as compared to control, will result in greater perceived emotional support at 6-weeks, 3, 6- and 12-months follow up;
- (c) For future implementation and dissemination, we will estimate the resources needed and costs to deliver ROSE. Additionally, we will estimate the incremental cost effectiveness of ROSE compared with treatment as usual.

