#### Primary Outcome Measure:

At baseline *frequency of IPV* for the past 12 months will be measured using the Composite Abuse Scale (CAS[60]). The CAS assesses the frequency of psychological, physical, sexual, and combined severe violence for each intimate relationship over a specified period of time. The CAS has demonstrated face, content, criterion, and construct validity[61]. The scale as a whole and its 4 subscales have all demonstrated good internal consistency and reliability[61]. The instrument will be administered at baseline and at each follow-up interval.

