**Costs:**

A secondary aim of this study will be to measure the total costs of ROSE vs. usual care for those at risk of IPV at participating study sites. Adhering to Second Panel on Cost-Effectiveness in Health and Medicine Guidelines[68], we will perform a cost-effectiveness analysis (CEA) to estimate the cost per IPV incident prevented by ROSE. Cost will be measured relative to usual care, with IPV reduction proxied by comparison to the research assistant blindable control condition that should be equivalent to usual care. We will collect data on three types of costs: 1) Implementation costs of establishing the ROSE program in a mental health clinic, including staff training time and resources, costs of hardware, software licensing, and adaptation of the program content to be relevant to the location; 2) Operational costs, including the human labor involved in identifying eligible patients, conducting screening, introducing patients to the program and demonstrating how to use it, obtaining follow-up information, and conducting the booster call, and 3) Participant costs in terms of time spent at the intervention and booster session, plus any travel costs related to intervention attendance, beyond the session where the person was screened. To record the first two sets of costs and distinguish them from research activities, the research assistants and the interventionist will track and log times for all study activities. The third set of costs will be captured by including questions about travel/waiting time, occupation, wage rate, and out-of-pocket expense in the survey at each added visit.

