**Costs:** RAs, interventionist, training, and supervisory time will be priced based on actual salaries, plus fringe benefits and overhead (drawn from institutional records), with sensitivity analysis on salaries at average wage rates for job titles nationally based on Bureau of Labor Statistics (BLS) annual Occupation and Employment Survey (OES) data. Participant time will be priced at the participant's hourly wage, with the state minimum wage used to price time of those who are not presently employed. This pricing approach is widely accepted[80]. Because treatment as usual has no cost and the incremental costs of treatment are directly measurable, power to detect a difference is not a consideration; the standard error of the added costs can be calculated directly and cannot overlap with \$0. Data from different years will be adjusted to same-year dollars using the appropriate Employment Cost Index from BLS for wages and the Consumer Price Index for other costs. The cost-effectiveness ratio will be computed as number

of IPV incidents prevented divided by total cost. To judge the CEA estimate, we will compare it to the average cost of an IPV incident. Bid economist [name] is about to submit a manuscript updating IPV costs based on recent data and an amalgam of his prior estimates and estimates for the Centers for Disease Control[81,82]. Our cost of an IPV includes the quality-adjusted life years lost to the incident, so it can be used to estimate a second cost-effectiveness ratio, namely the cost per quality-adjusted life year saved. The numerator in that calculation is intervention costs minus the medical and other direct (criminal justice) costs of the incident. The IPV costs include lifetime costs related to medical care and criminal justice, converted to present value using the 3% discount rate recommended by the PCEHM[68]. We will use the Crystal Ball® add-in to Excel to bootstrap standard errors for the cost-effectiveness ratios. We also will conduct one-way sensitivity analyses on non-probabilistic parameters, notably the discount rate and the wage rates of the clinical staff. NB: a much larger sample would be needed to directly track the cost of the IPV incidents.

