#### Data checking

Data will be collected using computer-based self-interview (ACASI) technology, and will only be identified with the study's ID of the participant. The PI will keep the link between the participant code number and name under lock-and-key. The accuracy with which data input matches data output using the software will be checked prior to beginning the trial and every five participants thereafter. Although no problems are expected given past experiences with this technology, any evidence of errors in data recording by the ACASI will result in dropping all participants since the last quality check. Data will be checked once per month for out of range values and other quality issues. [name] will analyze the data using SPSS software.

Primary outcomes of the Reach Out for a Safe Environment (ROSE) will be measures of the intervention's efficacy compared to a time, attention, and information matched control condition in reducing frequency of intimate partner victimization (IPV) at 6-weeks, 3-, 6- and 12-months after baseline assessment. Secondary outcomes will be measures of the ROSE efficacy compared to control in increasing positive affect and well-being and emotional support as well as collecting and measuring the cost effectiveness of ROSE to determine if sufficiently favorable. Tertiary aim will be to explore the role of theorized mediators of empowerment and self-efficacy on the effect of ROSE. Effect sizes with 95% confidence intervals will be calculated, and outcome data will be analyzed with alpha set at 0.05.

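### Secondary Aim 2c: the cost-effectiveness ratio is defined upside down, as incidents prevented per dollar, although the plan promises a cost per incident prevented and judges it in dollars per incident

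*Combined protocol and SAP*

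**What the plan says.** Aim 2(c) in section 1 states that "we will estimate the incremental cost effectiveness of ROSE compared with treatment as usual". The Costs paragraph in section 2 names the quantity: "we will perform a cost-effectiveness analysis (CEA) to estimate the cost per IPV incident prevented by ROSE".

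The Costs paragraph in section 4 gives the computing rule. The cost-effectiveness ratio is the number "of IPV incidents prevented divided by total cost". The next sentence gives the yardstick: "To judge the CEA estimate, we will compare it to the average cost of an IPV incident". The paragraph then adds a second ratio, cost per quality-adjusted life year (QALY) saved, and says of it: "The numerator in that calculation is intervention costs minus the medical and other direct (criminal justice) costs of the incident". Software is named "to bootstrap standard errors for the cost-effectiveness ratios". The same paragraph treats usual care as costless and says that the added cost cannot overlap zero.

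Under Data checking in section 4, the purpose is given as "measuring the cost effectiveness of ROSE to determine if sufficiently favorable".

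**The concern.** The two Costs paragraphs describe reciprocal quantities under one name. Section 2 wants dollars per incident, and section 4 computes incidents per dollar. The benchmark in section 4 is in dollars per incident, so the ratio and its yardstick have inverse units. The two ratios in section 4 also run in opposite directions: a low value is good for cost per QALY, and a high value is good for incidents per dollar. The plan does not say which side of the benchmark counts as favourable.

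At stake is the economic conclusion of Aim 2c, because this comparison is the yardstick that section 4 gives for the first ratio. The planned bootstrap standard error would also belong to the written ratio and not to the promised one. If the ratio is turned over only after the results are known, that is an undocumented departure from the plan.

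**Working it through.** The documents give no cost, incident or benchmark figure, so there is no stated result to reproduce. The check is one of units, followed by an illustration with assumed values.

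**1. Units.** Let C be the total cost of ROSE, E the incidents prevented and B the average cost of an incident.

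| Quantity | Where | Form | Unit |
|---|---|---|---|
| Promised estimate | Section 2, Costs | C/E | dollars per incident |
| Computed ratio | Section 4, Costs | E/C | incidents per dollar |
| Benchmark | Section 4, Costs | B | dollars per incident |
| Second ratio | Section 4, Costs | net cost / QALYs | dollars per QALY |

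Since (E/C) × (C/E) = 1, the computed ratio is exactly the reciprocal of the promised one. Of the four lines, only the computed ratio has cost underneath. Because usual care is taken to cost nothing, total cost equals incremental cost, so the difference is one of direction and not of cost concept.

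**2. Comparison with the benchmark.** Break-even means C/E = B, that is E/C = 1/B. Assume C = 20,000 dollars and B = 5,000 dollars, so 1/B = 0.0002 and break-even is at E = 20,000/5,000 = 4.

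| E | E/C (as written) | C/E (as promised) | C/E against B = 5,000 |
|---|---|---|---|
| 10 | 0.0005 | 2,000 | below, favourable |
| 4 | 0.0002 | 5,000 | equal |
| 2 | 0.0001 | 10,000 | above, unfavourable |

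Taken literally, every entry in the second column lies far below 5,000. The written ratio becomes usable if it is set against 1/B with the direction reversed (E/C above 0.0002 is favourable), but the plan does not say so.

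**3. Standard error.** Write R = E/C. To first order, SE(1/R) = SE(R)/R². The bootstrap standard error of the written ratio is therefore not that of the promised ratio, and the conversion fails as R approaches zero.

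**4. What the swap brings with it.** With cost on top, E moves to the denominator, and E may be near zero or negative. For E = −2 under the same assumptions, C/E = 20,000/(−2) = −10,000. This is below 5,000 although ROSE did worse than control. Incremental net benefit, B × E − C, has no such problem:

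- E = 10: 5,000 × 10 − 20,000 = 30,000
- E = 4: 5,000 × 4 − 20,000 = 0
- E = 2: 5,000 × 2 − 20,000 = −10,000
- E = −2: 5,000 × (−2) − 20,000 = −30,000

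**5. Scale.** The Power paragraph plans 93 women per arm and allows up to 20% drop-out (93 × 0.8 = 74.4, about 74). In the extreme case where one arm keeps 93 and the other 74, with the same mean of m incidents per woman, the raw totals differ by 93m − 74m = 19m with no effect at all. Incidents prevented should therefore be a difference of means per woman.

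**The case against.** The strongest reply is that this is a slip of wording. The promised quantity in section 2, the benchmark and the QALY ratio all point to cost divided by effect. The point estimate can be inverted without loss, and effect per dollar is a legitimate measure. An economist would notice that 0.0005 cannot be set against 5,000. The written form even has one advantage: its denominator, the added cost, stays away from zero.

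Most of this stands. It limits the consequence, and it is why the fix must do more than turn the fraction over. It does not remove the contradiction. The break in the sentence is only a page break, the words read on without a gap, and no other section corrects the rule or states the reversed comparison.

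A reader might infer that the economic result could not tell a favourable outcome from an unfavourable one. That follows only if the mismatch of units goes unnoticed, and section 2 gives enough to recover the intended quantity.

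A reader might also count the missing rule for deriving incidents from the Composite Abuse Scale (CAS) as part of this error. The plan says only that "The CAS assesses the frequency of psychological, physical, sexual, and combined severe violence for each intimate relationship over a specified period of time", and gives no conversion from score to incidents. That gap would be the same if the ratio were the right way up. It is a separate issue and does not measure this one.

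**Conclusion.** The point holds. The ratio in the Costs paragraph of section 4 is wrong as written: it is the reciprocal of what section 2 promises, has inverse units to its own benchmark, and runs opposite to the second ratio in the same paragraph. It should be corrected before the economic analysis is run.

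Its size is exactly that inversion. At break-even the written ratio is 1/B, while the text sets it against B. No further numerical size can be given, because the documents contain no cost or incident figure; the values of C, E and B above are assumptions for illustration only. The unit mismatch rests on the text alone.

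Only secondary Aim 2c is affected. The primary analysis of IPV frequency, the 5% significance level and the sample size of 186 do not use this ratio.

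**What to change.** In the Costs paragraph of section 4:

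- Define the ratio as the incremental cost of ROSE per woman divided by IPV incidents prevented per woman, the latter being the control mean minus the ROSE mean.
- State that, when incidents prevented exceed zero, a value below the average cost of an incident is favourable.
- From the same bootstrap resamples, report an interval for incremental net benefit per woman (average cost of an incident times incidents prevented, minus incremental cost). Do not rely on a standard error of the ratio alone.

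The cost is one clause reversed, two added sentences and slightly more analysis work. No new data are needed, and the sample size and primary analysis do not change. The change settles direction, units and scale only. How incidents are counted from the CAS needs its own statement.

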#### Data checking

Data will be collected using computer-based self-interview (ACASI) technology, and will only be identified with the study's ID of the participant. The PI will keep the link between the participant code number and name under lock-and-key. The accuracy with which data input matches data output using the software will be checked prior to beginning the trial and every five participants thereafter. Although no problems are expected given past experiences with this technology, any evidence of errors in data recording by the ACASI will result in dropping all participants since the last quality check. Data will be checked once per month for out of range values and other quality issues. [name] will analyze the data using SPSS software.

Primary outcomes of the Reach Out for a Safe Environment (ROSE) will be measures of the intervention's efficacy compared to a time, attention, and information matched control condition in reducing frequency of intimate partner victimization (IPV) at 6-weeks, 3-, 6- and 12-months after baseline assessment. Secondary outcomes will be measures of the ROSE efficacy compared to control in increasing positive affect and well-being and emotional support as well as collecting and measuring the cost effectiveness of ROSE to determine if sufficiently favorable. Tertiary aim will be to explore the role of theorized mediators of empowerment and self-efficacy on the effect of ROSE. Effect sizes with 95% confidence intervals will be calculated, and outcome data will be analyzed with alpha set at 0.05.

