After consent has been obtained, the RA will complete a locator form for the participant (if over the phone) or the participant will complete the form in the office. The baseline assessment will then be conducted on the phone or in-person. After the participant completes the screener assessment, is eligible for the RCT, has consented for the RCT, and has completed the baseline assessment, research staff will send a link to the intervention or will set up the intervention on the tablet at the hospital. The computer program will randomize participants into control vs. ROSE conditions. For participants coming to the hospital, optimal procedures to minimize risk of COVID-19 exposure will be used. At the time of screening, 3-month, 6-month, and 12-month assessments, we will as participants when their last appointment at WBH was.

Participants will be able to change their contact preferences at any point. Participants will be told they are able to drop out of the study at any point and that dropping out will not have any impact on the care that they receive at Women and Infants Hospital.

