**Power:** We calculated the sample size using mean, standard deviation, and within-subject correlation estimates for IPV frequency from our R21 study. IPV frequency was measured by the CAS Total score. In our pilot data, we observed participants in ROSE demonstrated a significantly larger change in frequency of IPV than the control condition. The observed between-group effect size for change in IPV frequency at follow up was moderate to large: Cohen's  $d$  of 0.59 and 0.68 with and without adjustment for baseline score. Therefore, a more conservative effect size of  $d = 0.4$  was selected for sample size estimation. With four follow up IPV assessments, a within-subject correlation of 0.62, and a standard deviation of 20, 74 participants per group are needed to detect an effect size of  $d = 0.4$  for the overall intervention vs. control group difference with 80% power at the 5% significance level. A minimum effect size of  $d = 0.4$  will be detectable for the secondary outcomes of positive affect and well-being and perceived emotional support. The secondary outcome measures are reported as T-scores based on a normative mean of 50 and standard deviation of 10. With 74 patients per group and assuming an observed SD of 10, a 4-point difference in positive affect and well-being or perceived emotional support will be detectable. Moderate effect sizes (Cohen's  $f$  for multiple regression = 0.39) for mediated effects of the intervention ( $\alpha$  and  $\beta$ ) will be detectable with 80% power and 74 patients per group[79]. For all the outcomes, our proposed sample of 186 should be adequate for detecting small to moderate effect sizes. Even assuming the worst-case scenario of up to 20% drop-out in both the ROSE and control groups, we plan to recruit 93 participants per arm.

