#### Data acquisition and transmission:

Data will be collected using computer-based self-interview technology (ACASI), and will only be identified with the study's ID of the participant. The use of computer technology for gathering self-report data further enhances overall protection. This software (ACASI) utilizes SSL technology for encrypting of communications between remote computers and the server itself, is HIPAA-compliant, and is currently used in a number of major NIH-funded research studies, including those of the PI.

At the Women and Infants Hospital research site, the link between the participant code number and name will be kept in a password protected file on password protected computer. The accuracy with which data input matches data output using the software will be checked prior to beginning the trial and every five participants thereafter. Data will be checked once per month for out of range values and other quality issues. ACIAS data is password protected and only research personnel will be able to access. Results and the response to whether or not she agrees to participate in the study will be transferred by secure, encrypted electronic file and downloaded to a secure Women and Infants Hospital server. Importantly, no identifying information will be entered into the ACASI. [name] will analyze the data using SPSS software. Booster session data will be recorded using a credit-card size digital audio recorder with data encryption capabilities, which can hold hundreds of hours of

voice recordings so that adherence and competence ratings of the booster sessions can be conducted. These digital recordings which will be labeled with the study identification number and the booster session date and will be transferred to Women and Infants Hospital secure computer server via a secure server access. Access to the audio recordings will be limited to research staff.

Data will be destroyed two years after the completion of the study. We expect the study to be completed by 2024, so we expect the data to be destroyed in 2026.

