## 6. WITHDRAWAL OF SUBJECTS

Study staff will be trained on understanding the various potential risks of participation in this study, as explained above, in the section "Risks and Benefits." As explained in this section, various procedures will be put into place to mitigate these potential risks. However, if when discussing the safety of a subject's participation in the study, study staff decides that stopping a subject's participation is necessary for safety reasons, then study staff will withdraw the subject from the study. As explained in the "Risks and Benefits" section, we anticipate that potential circumstances in which this might need to occur include breaching of confidentiality, coercion of participants, participant discomfort, the occurrence of study-related partner violence, and/or social or legal consequences related to study participation.

If participants voluntarily withdraw from the research, study staff will keep the data that has already been collected, and will use this data in the study analysis procedures. If a participant is physically present when she decides to withdraw from the study, she will be checked in with by research staff, be given any relevant informational handouts if it is safe for her to receive and take with her, and be given any relevant referrals.

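### If any ACASI recording error is found, the data-checking rule removes every participant since the last check, including randomised women whose own records are sound

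*Combined protocol and SAP*

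**What the plan says.** Under section 4, the Data checking section says that the match between data entered and data stored by the software "will be checked prior to beginning the trial and every five participants thereafter". It adds that problems are not expected, given past experience with the technology, but that "any evidence of errors in data recording by the ACASI will result in dropping all participants since the last quality check".

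The section on data acquisition and transmission describes the same check ("The accuracy with which data input matches data output using the software will be checked prior to beginning the trial and every five participants thereafter") and states no consequence if it fails.

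Other parts of the plan that bear on the rule:

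- **Recruitment Methods and Informed Consent Process.** The baseline assessment comes first. The intervention is then opened, and "The computer program will randomize participants into control vs. ROSE conditions".
- **Primary Outcome Measure.** For the CAS, "The instrument will be administered at baseline and at each follow-up interval".
- **Data Collection Procedures.** Follow-up measures are given by a research assistant, by phone or at the hospital. The Objectives and the two data sections describe computer-based collection instead.
- **Missing Data.** The method is an inverse-probability-weighted analysis of complete cases. It does not mention women removed by the study.
- **Withdrawal of Subjects.** For women who withdraw voluntarily, "study staff will keep the data that has already been collected, and will use this data in the study analysis procedures".
- **Power.** The recruitment target of 93 per arm allows for drop-out only: "Even assuming the worst-case scenario of up to 20% drop-out in both the ROSE and control groups".

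The one reference to intent to treat stands in the Adequacy of Sample Size text about 50 participants. No analysis set is defined for the 186-woman trial.

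**The concern.** The trigger is any recording error, and the unit removed is the woman rather than the item, record or visit. Nothing requires that her own data be wrong, that the primary outcome be touched, or that correction be tried first. A fault in one record would remove the others in the window with it. Because randomisation follows directly on the baseline assessment, these would normally be randomised women.

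At stake are the principle that women are analysed as randomised, and the loss of sound CAS data. What counts as evidence of an error is undefined, and the documents do not say that whoever runs the check is unaware of allocation. If errors, or the chance of finding them, differed by arm, device or delivery mode (online or on site), the exclusions could be informative. The sample-size allowance also makes no provision for women removed by the study itself.

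**Working it through.** **Inputs (Power paragraph).** SD 20; within-subject correlation 0.62; four follow-ups; d = 0.4, so the difference is 0.4 × 20 = 8 points; 5% significance (two-sided assumed, as the sidedness is not stated); 80% power; 74 per group; 20% drop-out; 93 per arm. The check interval of five participants is from Data checking.

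**Reproducing the plan's figures.** The variance of a woman's four-visit mean is 400 × (1 + 3 × 0.62)/4 = 286.

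The number per group is 2 × (1.960 + 0.842)² × 286/8² = 70.1, so 71 by the normal approximation, or 72 with the noncentral t. The plan states 74, which is close and slightly conservative. With three visits the variance is 400 × (1 + 2 × 0.62)/3 = 298.7, which gives 73.3, so exactly 74.

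The recruitment figure reproduces: 74/0.8 = 92.5, rounded up to 93. After 20% drop-out, 186 × 0.8 = 148.8 women are expected (74.4 per arm), against 2 × 74 = 148 required.

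**Effect of the rule.** Let k be the number of failed checks. The documents give no error rate, so k is an assumption. If the window counts enrolled women, each failed check removes up to 5, which is 5/186 = 2.7%. The expected number per arm is n = (186 − 5k) × 0.8/2. Power is approximately Φ(8/√(2V/n) − 1.96), with V = 286 for four visits and V = 298.7 for three.

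| k (assumed) | Women removed | Expected total | n per arm | Power, four visits | Power, three visits |
|---|---|---|---|---|---|
| 0 | 0 | 148.8 | 74.4 | 82.3% | 80.6% |
| 1 | 5 (2.7%) | 144.8 | 72.4 | 81.2% | 79.5% |
| 2 | 10 (5.4%) | 140.8 | 70.4 | 80.1% | 78.4% |
| 3 | 15 (8.1%) | 136.8 | 68.4 | 79.0% | 77.3% |
| 4 | 20 (10.8%) | 132.8 | 66.4 | 77.8% | 76.0% |
| 5 | 25 (13.4%) | 128.8 | 64.4 | 76.6% | 74.8% |

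With the four visits that the plan states, the cost is about 1 point per failed check. If the window also takes in women who had a follow-up visit during it, each loss is larger; the text does not settle this.

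**Does any other text limit the rule?** None does. The data acquisition section repeats the check but not the consequence. The missing-data method does not cover women removed by the study, and no analysis set overrides the rule.

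**The case against.** The strongest reply is that the rule may never act. The plan expects no errors, and with none the effect is nil. There is also a rationale: once a recording fault is found, everything since the last clean check is unverified, and the documents name no second source for self-interview answers. Both points are fair. Neither justifies removing whole women: doubt about one window of recordings is a reason to set those recordings aside, not a woman's other visits.

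Four stronger readings are tempting, and the documents do not support them.

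- **That the rule biases the comparison.** Nothing ties the trigger to arm or outcome. Bias is a possibility that depends on errors or their detection differing by arm, device or delivery mode.
- **That the sample size has no slack.** In head count, one failed check does take the expected total below 148. In power, two failed checks on top of the full drop-out still leave about 80% with four visits. Only under the three-visit variance, which is not what the plan states, does one failed check go just below 80%.
- **That the rule contradicts the withdrawal section.** That section concerns women who choose to leave and whose data are not in doubt. It is a contrast in principle, not a conflict.
- **That follow-up CAS data are certain to be lost.** If the five participants are counted at enrolment, many women in a window may have only baseline data when the check is made. The text does not say whether dropping means from the study or from the analysis, or how the rule works at follow-up visits. How much of the outcome data passes through ACASI is also unclear. Either sense of dropping still excludes randomised women.

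**Conclusion.** The point holds as a fault in a stated rule whose harm is contingent. If the rule is triggered and followed as written, randomised women are excluded whether or not their own record or the CAS was affected, and usable data are discarded. That departs from analysis as randomised. Bias is possible, not established.

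The size is up to about 5 women (2.7% of 186) per failed check, on the reading that the window counts enrolled women. Power falls about 1 point each time, from about 82% at 74 per arm to 80% at 70 and 78% at 66. These figures assume the full 20% drop-out, the plan's own inputs with four visits, a two-sided test and a normal approximation; the number of failed checks is an assumption throughout. The case for change rests on exclusion after randomisation and on how easily the wording can be put right, not on power.

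**What to change.** Replace the sentence in Data checking with a rule on these lines:

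1. When a check finds an error, review all records since the last check and correct values where a source exists.
2. Set to missing only the affected items or visits that cannot be recovered.
3. If it cannot be established which records are affected, set the ACASI-recorded data in that window to missing for that visit only, and do not drop the woman.
4. Keep every randomised woman in the analysis with all her unaffected visits, and log each error.

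State the same rule in the data acquisition and transmission section, so that the two descriptions agree.

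The Missing Data paragraph must change as well. Because it is confined to complete cases, a participant-level reading would still exclude a woman with one visit set to missing. It should say that the weighted analysis works at visit level, so that one missing visit does not remove her other visits from the mixed model.

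The cost is a short record review after each detected error and small wording changes in three places. No additional participants are needed.
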